6 TRIAL DESIGN

6.1 Overall Trial Design

This is a multi-centre, open-label, single-arm trial investigating the safety and efficacy of C21 in which subjects with IPF will be treated for a maximum of 36 weeks. In total, approximately 60 subjects will be recruited.

To ensure careful and ongoing evaluation of the individual risk/benefit profiles, each subject will undergo a medical evaluation by the investigator at the end of every 12-week treatment period, where the investigator will evaluate if continuation into the next 12-week treatment period is considered safe for the individual subject.

In addition, throughout the duration of the trial, an independent data monitoring committee (IDMC) will evaluate all serious adverse events (SAEs) on an ongoing basis in accordance with the IDMC charter. The IDMC will monitor all available safety data during regular meetings as

Clinical Trial Protocol

Vicore Pharma AB
Trial ID: VP-C21-005

Version: 7.0
Date: 15-Sep-2021

defined in the IDMC charter and provide appropriate recommendations to the Sponsor on the overall safety of trial participants (see Section 14).

The subjects will attend up to 15 visits to the clinic:

- Visit 1: Screening
- Visits 2 – 7: Treatment period 1
- Visits 8 – 11: Treatment period 2
- Visits 12 – 14: Treatment period 3
- Visit 15: End-of-trial

IMP will be administered as home treatment twice daily (*b.i.d.*) during all treatment periods 1-3.

Final safety follow-up assessments at Visit 15 (end of trial visit), must be performed for all subjects who have received trial treatment. Visit 15 must be scheduled 2-4 weeks after the last IMP administration (see Section 7.3).

The maximum duration of the trial for any subject will be approximately 44 weeks, including a screening period of up 4 weeks, a treatment period up to 36 weeks and a visit for safety follow up to be conducted maximum 4 weeks after the last dose of IMP (please see clinical trial design in Figure 1).

6.2 Number of Subjects

The trial will enroll a sufficient number of subjects to ensure at least 60 subjects with a completed 12-week visit.

Clinical Trial Protocol

Vicore Pharma AB
Trial ID: VP-C21-005

Version: 7.0
Date: 15-Sep-2021

6.3 Trial Diagram

[figure not shown]

Figure 1. VP-C21-005 Clinical Trial Design

6.4 Trial Duration and Participating Centers

Planned first subject screened: Q3 2020

Planned last subject enrolled: Q1 2022

Planned last subject last visit: Q1 2023

The end of trial date is defined as the date the last subject attends the last visit.

The trial will be conducted at trial sites globally.

6.5 Schedule of Events

6.5.1 Screening (Visit 1)

Prior to and no later than at start of screening (Visit 1) i.e. before any trial related activity takes place, the investigator or a qualified designee will explain the nature of the trial, its purpose, the procedures involved, the expected duration, the potential risks and benefits involved, and any discomfort it may entail. All explanations shall be in layman's language. The subject will be provided with a copy of the information sheet. The subject must be given sufficient time to consider the trial before deciding whether to participate.

After signed informed consent is obtained from the subject, the screening procedures can be initiated.

Clinical Trial Protocol

Vicore Pharma AB
Trial ID: VP-C21-005

Version: 7.0
Date: 15-Sep-2021

All subjects giving informed consent to participate in the trial will receive a screening number. During the screening visit, the subject is evaluated for eligibility (please refer to Section 5.1 and 5.2).

The following procedures are performed:

- Written Informed Consent to be obtained
- Assignment of screening number
- Pregnancy testing (beta-HCG)
- Check of in- & exclusion criteria
- Assessment of eligibility which includes review of demographics, medical history, concomitant illnesses and medication, COVID-19 vaccination status, physical examination, height, weight, BMI and measurement of blood pressure, pulse and body temperature
- Medical history and concomitant medication
- 12-lead ECG
- Spirometry
- SpO₂
- HRCT to be collected and sent for central review
- Slit lamp examination to be performed prior to Visit 2
- Blood sampling for HBsAG, HCVab, HIV 1+2 Ag/Ab and safety (See Table 1 and Section 8)
- Urinalyses (dipstick) for bilirubin, glucose, ketones, protein, specific gravity, urobilinogen, pH
- Information on restrictions prior to IMP administration (see Section 5.3)
- Reporting of adverse events (AEs)

6.5.2 Treatment Periods (Visits 2-14)

The total treatment period may last for maximum 36 weeks, comprising three 12 week treatment periods. At the end of treatment period 1 (Visit 7) and treatment period 2 (Visit 11), a medical evaluation is performed by the investigator to assess if treatment can be continued for an additional 12 weeks (see Section 5.4.1)

- Treatment period 1 (Visit 2-7)
 - Subjects will attend the clinic every 2 weeks for the first 6 weeks (Visit 2-5) and subsequently every 3 weeks for the last 6 weeks (Visit 6-7)
- Treatment period 2 (Visit 8-11)
 - Subjects will attend the clinic every 3 weeks for 12 weeks (visit 8-11)
- Treatment period 3 (Visit 12-14)
 - Subjects will attend the clinic every 4 weeks for 12 weeks (Visit 12-14)

The procedures to be performed at each visit are specified below.

Visit 2

Clinical Trial Protocol

Vicore Pharma AB
Trial ID: VP-C21-005

Version: 7.0
Date: 15-Sep-2021

Visit 2 can be scheduled as soon as the relevant screening assessments are available. Visit 2 must occur 3-30 days from Visit 1 (screening) to ensure that no eligibility assessments are older than 30 days when treatment is initiated.

The following procedures are performed:

- Re-evaluation of in- & exclusion criteria (including physical examination, assessment of vital signs, ECG, spirometry, slit lamp and laboratory results from Visit 1)
- Concomitant medication
- Pregnancy testing (beta-HCG)
- Assignment of enrollment number
- 12-lead ECG
- Holter ECG
- Blood sampling for safety and biomarker assessments (See [Table 1](#) and [Section 8](#))
- Urinanalysis (dipstick for bilirubin, glucose, ketones, protein, specific gravity, urobilinogen and pH)
- Spirometry
- IMP administration
- PK sampling
- Hand-out of medication
- Re-instructions regarding dietary restrictions prior to IMP administration (see [Section 5.4](#))
- Reporting of AEs

Visits 3-14

- Concomitant medication
- Pregnancy testing (urine dipstick)
- Physical examination, (including body weight and vital signs)
- Blood sampling for safety
- 12-lead ECG
- Urinanalysis (dipstick for bilirubin, glucose, ketones, protein, specific gravity, urobilinogen and pH)
- Spirometry
- Return of medication
- IMP compliance check
- Drug accountability
- Hand-out of medication (not applicable for visit 14)
- Re-instructions regarding dietary restrictions prior to IMP administration (see [Section 5.4](#).
Not applicable for visit 14)
- Reporting of AEs

Additionally for Visit 7, 11 and 14 (end of each 12 week treatment period)

- Medical evaluation by investigator for continued treatment with C21 for an additional 12 weeks (Visits 7 and 11 only)

Clinical Trial Protocol

Vicore Pharma AB
Trial ID: VP-C21-005

Version: 7.0
Date: 15-Sep-2021

- Blood sampling for PK analyses prior to the morning dose and at 30 min, 1 hour, 2 hours, 3 hours and 4 hours post-dose in a selected group of 20 subjects
- Blood sampling for exploratory biomarker analyses

6.5.3 End-of-Trial (Visit 15)

Visit 15 is performed minimum 2 weeks and maximum 4 weeks after the last IMP administration.

The following procedures are performed:

- Recording of concomitant medication
- 12-lead ECG
- Blood sampling for safety and biomarker assessments (See [Table 1](#) and Section [8](#))
- Urinalysis
- Pregnancy test (beta-HCG)
- Physical examination including body weight (See [Table 1](#) and Section [8.2.4](#))
- Vital signs
- Spirometry
- Slit lamp examination
- Concomitant medication
- Reporting of AEs

If a subject is withdrawn from treatment (see Section [5.7](#)), a Visit 15 (end-of-trial visit) must be performed.

Clinical Trial Protocol

7 TRIAL TREATMENT

7.1 Investigational Medicinal Product

C21 is presented as a capsule for oral administration. The drug substance is [REDACTED]

[REDACTED] 50-mg C21 oral capsule.

Table 3 Qualitative and Quantitative Composition of the IMP

[REDACTED]	[REDACTED]	[REDACTED]	[REDACTED]	[REDACTED]
[REDACTED]	[REDACTED]	[REDACTED]	[REDACTED]	[REDACTED]
[REDACTED]	[REDACTED]	[REDACTED]	[REDACTED]	[REDACTED]
[REDACTED]	[REDACTED]	[REDACTED]	[REDACTED]	[REDACTED]
[REDACTED]	[REDACTED]	[REDACTED]	[REDACTED]	[REDACTED]
[REDACTED]	[REDACTED]	[REDACTED]	[REDACTED]	[REDACTED]
[REDACTED]	[REDACTED]	[REDACTED]	[REDACTED]	[REDACTED]

7.2 Packaging, Labelling and Storage

IMP will be delivered as 50 mg capsules packed in plastic container units with 56 capsules in each. Each unit will be labelled in local language.

At the trial site, IMP must be stored separately from normal clinic stocks in a securely locked area only accessible to authorised trial personnel. Storage temperature must be monitored and kept at room temperature (15-25° C).

Labeling of the IMP will be done in compliance with Good Manufacturing Practice (GMP) Annex 13 ([GMP 2003](#)) and local regulatory requirements.

IMP will be dispensed to subjects at Visits 2-13. The subjects will be instructed to store the IMP at room temperature (15-25° C) in their own homes.

7.3 IMP Administration

IMP will be administered twice daily by the subject at home as follows:

- Morning dose: Two 50 mg capsules (100 mg C21) to be taken with a glass of water after minimum 2 hours fasting
- Afternoon/evening dose: Two 50 mg capsules (100 mg C21) to be taken with a glass of water after minimum 2 hours fasting

Subjects will be required not to eat anything for 1 hour after taking the C21 capsules.

Clinical Trial Protocol

Vicore Pharma AB
Trial ID: VP-C21-005

Version: 7.0
Date: 15-Sep-2021

7.4 Compliance Check and Drug Accountability

Compliance with C21 administration will be assessed by capsule count performed by the trial staff at visits 3-14. Details of the capsule count and compliance check will be recorded in the patient medical record.

After IMP accountability has been completed, all unused and partly used IMP will be returned to the Sponsor or Sponsor's designee for destruction. All returned IMP will be reconciled.

7.5 Blinding of the Trial

Not applicable.

7.6 Procedures for Unblinding

Not applicable.

7.7 Prior and Concomitant Medications

Concomitant medications are all medications being continued by the subject at trial entry, and all medications 4 weeks prior to screening and received in addition to IMP during the trial period.

At each visit, the investigator or qualified designee will ask the subject about concomitant medication. All concomitant medications will be documented in the subject's medical records and in the electronic case report form (eCRF). Any changes in concomitant medications (e.g. new treatment, discontinuation of treatment or change in dosage) during the trial period must be documented in the subject's medical records and in the eCRF.

The following information will be recorded in the eCRF:

- Generic name (preferred) or trade name
- Reason for prescription
- Dose unit and frequency
- Route of administration
- Start date (if started > 3 months prior to Visit 1, then this can be stated instead of recording a date)
- Stop date (unless ongoing at trial termination)

7.7.1 Allowed Concomitant Medication

If considered unlikely to interfere with IMP or the outcome of the trial results, concomitant medication may be given according to local standard of care.

In addition, the following medications are allowed:

- Inhaled corticosteroids provided the dose is kept stable throughout the trial period
- Stable daily dose of ≤ 15 mg prednisolone, or equivalent.
- Corticosteroids for the treatment of acute exacerbations
- PPIs if once daily and taken 1 hour after the morning dose of C21

7.7.2 Disallowed Concomitant Medication

The following treatments are not allowed:

Clinical Trial Protocol

Vicore Pharma AB
Trial ID: VP-C21-005

Version: 7.0
Date: 15-Sep-2021

4 weeks before Visit 1 and during the trial period	
Strong CYP3A4 inducers (e.g. rifampicin, phenytoin, St John's Wort)Strong CYP3A4 inhibitors (e.g. clarithromycin, ketoconazole, nefazodone, itraconazole, ritonavir)Medicines that are substrates of CYP1A2, CYP3A4 or CYP2C9 with a narrow therapeutic range¹⁾Experimental drugsAny systemic immunosuppressive therapy other than:
Inhaled corticosteroids which can be used throughout the trial periodThe continuation of a stable daily dose of <15 mg prednisolone, or equivalentAntifibratics (e.g. nintedanib, pirfenidone)
2 weeks before Visit 1 and during the trial period	
PPIs more than once dailyH2RAsSulphasalazine, rosuvastatinHigh dose breast cancer resistance protein sensitive substrates (other than sulphasalazine or rosuvastatin)
12 hours before spirometry/FVC assessments	Long acting bronchodilators
4 hours before spirometry/FVC assessments	Short acting bronchodilators
Throughout the duration of the trial	
Systematic and continuous use of PPIs more than once daily and H2RA medications

¹⁾ e.g. alfentanil, astemizole, cisapride, cyclosporine, dihydroergotamine, ergotamine, fentanyl, phenytoin, pimozide, quinidine, sirolimus, tacrolimus, theophylline, pirfenidone, celecoxib and warfarin. Investigators will need to consult the product information of a concomitant drug as these lists may not be exhaustive.

8 ASSESSMENTS

8.1 Efficacy Assessments

8.1.1 Spirometry

Throughout the trial, spirometry will be performed using equipment provided to all sites by the Sponsor, who will ensure that the equipment meets the minimal ATS/ERS recommendations for diagnostic spirometry equipment as defined in the guideline ([Miller et al. 2005](#)).

All spirometry reports will be stored as source data (see Section 11.2).

Spirometry procedures will be performed according to a manual. To reduce variability every effort should be made to assure consistent testing conditions throughout the trial:

- The same spirometry equipment should be used for all assessments performed by a subject within the trial
- All staff conducting the spirometry tests must have received appropriate training which must be documented

Clinical Trial Protocol

Vicore Pharma AB
Trial ID: VP-C21-005

Version: 7.0
Date: 15-Sep-2021

- Whenever possible the same technician should perform all manoeuvres for an individual subject.
- Whenever possible, spirometry should be conducted at the same time of day (+/-1 hour) as the baseline measurement

The subject's gender, age and height as reported at Visit 1 are entered into the spirometer and will be used throughout the trial.

Spirometry is an effort-dependent test which requires careful instruction and cooperation of the subject. The subject is recommended to be positioned in a seated position with nose clip to reduce risks related to dizziness or syncope. The technician should ensure that the subject maintains a good seal around the mouthpiece and confirm that the subject's posture is correct. The subject should be instructed to perform tidal breathing followed by a maximal inspiration until no further air can be inhaled, followed rapidly by maximum forced expiration until no more air can be exhaled or the volume time curve displays a plateau marked by flow rates of <25ml/sec for at least one second. This should be followed by a maximal inspiration. Expiration must be rapid with exertion of maximal effort. The results of spirometry should meet the ATS/ERS criteria 2005 (Miller et al. 2005) for acceptability and repeatability.

The highest FVC and FEV₁ from any of the acceptable curves are recorded. The highest FVC and FEV₁ may not necessarily result from the same acceptable curve.

Spirometry data will be assessed by a central reader for quality control and be classified for acceptability. In addition an assessment for plausibility will be performed.

8.1.2 Biomarkers

Blood samples for potential analysis of biomarkers related to inflammation and fibrosis will be obtained at Visit 2 and the end of each treatment period (Visits 7, 11, 14 and 15).

Details of sampling and storage will be specified in the laboratory manual.

8.1.3 Pharmacokinetics

Blood samples for pharmacokinetic will be analysed in a subset (20) of subjects. The samples will be collected at Visit 2, and at the end of each treatment period at Visit 7, Visit 11 and Visit 14 prior to the morning dose and at 30 min, 1 hour, 2 hours, 3 hours, and 4 hours post-dose.

8.2 Safety Assessments

8.2.1 Adverse Events

Adverse events (AEs) will be reported from signing of informed consent until end-of-trial participation (Visit 15).

8.2.2 Medical History and Concomitant Illnesses

The medical history including date of first diagnosis of disease under study and concomitant illnesses will be obtained by interviewing the subject or by checking his/her medical records.

Clinical Trial Protocol

Vicore Pharma AB
Trial ID: VP-C21-005

Version: 7.0
Date: 15-Sep-2021

8.2.3 Pregnancy Test

Women of childbearing potential will undergo pregnancy tests at all visits ¹⁾.

- Visit 1, 2 and Visit 15: Blood sample
- Visit 3 -Visit 14: Urine dip-stick

1) Women of non-childbearing potential are defined as pre-menopausal females who are sterilised (tubal ligation or permanent bilateral occlusion of fallopian tubes); or post-menopausal defined as 12 months of amenorrhea (in questionable cases a blood sample with simultaneous detection of Follicle-stimulating Hormone 25-140 IE/L and oestradiol <183 pmol/l is confirmatory).

8.2.4 Physical Examination

A complete physical examination including assessments of the head, eyes, ears, nose, throat, skin, thyroid, neurological, lungs, cardiovascular, abdomen (liver and spleen), lymph nodes, and extremities will be performed at Visit 1, 2, and Visit 15.

A short version of the physical examination including assessments of selected body systems at the judgement of the investigator will be performed at all other visits (3-14) and must include a cardiovascular examination.

Each body system will be reported as “normal”, “abnormal – non clinically significant” or “abnormal –clinically significant”. Any clinically significant abnormalities prior to initiation of IMP should be specified and recorded as medical history. New clinically significant abnormalities occurring after initiation of IMP should be reported as AEs.

8.2.5 Vital Signs

Systolic and diastolic blood pressure, pulse, and body temperature will be measured in supine position after 10 minutes of rest.

8.2.6 Electrocardiogram

12-lead electrocardiography (ECG) will be recorded at all visits to the clinic (Visit 1-15).

Holter ECG will be recorded at Visit 2 from at least 30 mins prior to IMP administration until at least 180 mins after.

ECG evaluations will be performed by a central reader.

Any clinically significant ECG abnormalities prior to initiation of IMP should be specified and recorded as medical history. New clinically significant abnormalities occurring after initiation of IMP should be reported as AEs.

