- 3) Historical high-resolution computed tomography (HRCT) no older than 36 months from date of Visit 1 will be collected for central review prior to enrolment
- 4) A complete physical examination will be performed at Visit 1, 2 and 15. At Visits 3-14 only a short physical examination will be performed (see Section 8.2.4)
- 5) All ECGs will be centrally reviewed
- 6) Slit lamp examination is to be performed by an ophthalmologist prior to Visit 2 and at Visit 15, where the results will be reviewed by the investigator
- 7) Medical evaluation by investigator for continued treatment with C21 for an additional 12 weeks
- 8) For spirometry measurements, gender, height and age values obtained at Visit 1 are used. FEV₁ and FVC values are obtained as described in Section 8.1.1
- 9) Re-instruct subjects on dietary requirements (see Section 5.4) and prohibited medication (see Section 5.2)

Clinical Trial Protocol

Vicore Pharma AB
Trial ID: VP-C21-005

Version: 7.0
Date: 15-Sep-2021

Visit	Screening			Treatment Period 1					Treatment Period 2					Treatment Period 3			End-of-Trial 1)
	Visit 1	Visit 2	Visit 3	Visit 4	Visit 5	Visit 6	Visit 7	Visit 8	Visit 9	Visit 10	Visit 11	Visit 12	Visit 13	Visit 14	Visit 15	Visit 15	
Visit Number	-1	0	2	4	6	9	12	15	18	21	24	28	32	36	40		
Week Number																	
Laboratory Sampling																	
HCV Ab	x																
HBsAg	x																
HIV 1+2 Ab/Ab	x																
Biochemistry	x	x	x	x	x	x	x	x	x	x	x	x	x	x	x	x	
Haematology	x	x	x	x	x	x	x	x	x	x	x	x	x	x	x	x	
Urinalysis ¹⁰⁾	x	x	x	x	x	x	x	x	x	x	x	x	x	x	x	x	
Expl. biomarkers	x												x	x	x	x	
Pregnancy testing ¹¹⁾	x ¹²⁾	x ¹²⁾	x	x	x	x	x	x	x	x	x	x	x	x	x	x	
Pharmacokinetics ¹³⁾	x											x	x	x	x	x	

10) Urinanalysis: Dipstick for bilirubin, glucose, ketones, protein, specific gravity, urobilinogen and pH

11) Only applicable for female subjects of childbearing potential, as defined in Section 5.3.1.

12) At Visit 1, 2 and 15 blood tests (beta-HCG) are performed for pregnancy. At Visits 3-14 urine dipsticks are performed

13) Collection prior to morning dose and at 30 min, 1 hour, 2 hours, 3 hours and 4 hours post-dose in a selected group of 20 subjects.

Clinical Trial Protocol

Vicore Pharma AB
Trial ID: VP-C21-005

Version: 7.0
Date: 15-Sep-2021

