9.3 Reporting of Adverse Events

All events meeting the definition of an AE must be reported in the period from the subject has signed the informed consent form until the end of trial participation (Visit 15).

At each visit the subject will be asked about AEs in an objective manner, e.g.: “Have you experienced any problems since the last visit?”

Only medically qualified personnel (investigators) must assess AEs.

Clinical Trial Protocol

Vicore Pharma AB
Trial ID: VP-C21-005

Version: 7.0
Date: 15-Sep-2021

AEs must be reported on the AE form. In the eCRF the diagnosis should be recorded, if available. If no diagnosis is available each sign and symptom should be recorded as individual AEs.

AEs concerning cardiac or ophthalmic conditions are of special interest and must be reported to the Sponsor within 24 hours of obtaining knowledge of the event.

SAEs, in addition, must be reported within 24 hours of obtaining knowledge of the event. The information to be reported will include assessment of severity, causal relationship to IMP or trial procedures, action taken, outcome, and a narrative description of the course of the event. Additional information may be subsequently provided.

The SAE form and all other relevant documents supporting the reported SAE (e.g. diagnostic procedures, hospital records, autopsy reports) must be faxed or scanned/mailed to the Sponsor or Sponsor's designee.

The independent ethics committees (IEC) and regulatory authorities will be notified of SAEs according to current regulation and local requirements.

All suspected unexpected serious adverse reactions (SUSARs) are subject to expedited reporting to regulatory authorities.

The expectedness of a SUSAR will be assessed against the reference safety information. Any SUSARs will be reported by the clinical research organisation (CRO) to the relevant competent authority. SUSARs will also be reported to the IEC by the site/CRO. Fatal and life threatening SUSARs will be reported as soon as possible and no later than seven calendar days from the date of first knowledge of the event. Relevant follow-up information will subsequently be expedited within an additional eight days. All other SUSARs will be expedited no later than 15 calendar days of first knowledge of the event.

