13.4 Safety Analysis

13.4.1 Adverse Events

An overview of all treatment-emerging AEs including severity, relationship to IMP, serious AEs (SAEs) and AEs leading to withdrawals of treatment and withdrawal from trial or death will be presented by treatment group.

AEs will be summarised by treatment group, system organ class (according to MedDRA), and preferred term (according to MedDRA) displaying number of subjects in treatment group, number and percentage of subjects having the AE as well as number of AEs. Furthermore, AEs will be summarised according to severity, relationship, outcome, and seriousness.

SAEs and AEs leading to withdrawal from treatment will be listed and tabulated, if appropriate.

Clinical Trial Protocol

Vicore Pharma AB
Trial ID: VP-C21-005

Version: 7.0
Date: 15-Sep-2021

13.4.2 **Electrocardiogram**

12-lead ECG data will be summarised by visit including the change from baseline. The number of abnormal assessments will be summarised by visit and for changes from baseline to end-of-trial.

13.4.3 **Vital Signs**

Vital signs data (blood pressure and pulse) will be summarised by visit including the change from baseline.

13.4.4 **Laboratory Safety Assessments**

Continuous laboratory data will be summarised by visit including the change from baseline. Categorical data will be summarised by visit using frequency and percentages. Laboratory parameters will be categorised as ‘low’, ‘normal’ or ‘high’ (*i.e.* below, within, or above the reference ranges, respectively) and summarised by visit and for changes from baseline to end-of-trial in a shift table.

13.4.5 **Physical examination**

Abnormal findings on the physical examination will be summarised by visit.

14 **INDEPENDENT DATA MONITORING COMMITTEE**

An independent data monitoring committee (IDMC) has been established and will have their first meeting before the trial starts.

The functions and responsibilities of the IDMC is described in an IDMC charter.

Throughout the duration of the trial, the IDMC will evaluate all SAEs on an ongoing basis.

Further, the IDMC will monitor the overall safety of the trial during regular meetings and provide appropriate written recommendations to the Sponsor regarding trial continuation, protocol modifications or trial suspension.

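### ECGs under repeated dosing have no stated timing relative to the dose, and the one dose-timed recording (the first-dose Holter) has no planned summary: a cheap improvement

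*Combined protocol and SAP*

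**What the plan says.** Section 8.2.6 (Electrocardiogram) gives the Holter a window around dosing: "Holter ECG will be recorded at Visit 2 from at least 30 mins prior to IMP administration until at least 180 mins after". Section 6.5.2 lists the Holter at Visit 2 only. Section 8.2.6 also schedules a 12-lead ECG at every clinic visit from 1 to 15, with no time relative to dosing. The flow chart's ECG footnote in Section 2 says only that "All ECGs will be centrally reviewed", and the procedure list for Visits 3 to 14 in Section 6.5.2 adds no timing.

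On dosing, Section 7.3 states: "IMP will be administered twice daily by the subject at home as follows". For a subset of 20 subjects, Section 8.1.3 schedules blood samples at Visits 2, 7, 11 and 14, "prior to the morning dose and at 30 min, 1 hour, 2 hours, 3 hours, and 4 hours post-dose". No ECG is linked to those samples.

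On analysis, Section 13.4.2 states: "12-lead ECG data will be summarised by visit including the change from baseline". It also counts abnormal assessments. It does not mention time since dose, and neither it nor the rest of Section 13.4 mentions the Holter.

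**The concern.** The protocol gives cardiac safety some weight. Section 3.7 makes safety the primary objective because patients receive repeated doses of C21 for the first time in this trial. Section 5.2 excludes subjects with QTcF above 450 ms. Section 9.3 says that "AEs concerning cardiac or ophthalmic conditions are of special interest" and asks for them to be reported within 24 hours.

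An ECG effect that follows plasma concentration can be judged only if the time since the last dose is known. If tracings from unknown points in the dosing interval are averaged by visit, a mean change near zero has two explanations: no effect, or tracings taken away from the peak. The planned data do not separate them. At stake is how far the trial report can interpret its own repeated-dose ECG tables. Subject protection during the trial is a different matter and rests on other measures.

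**Working it through.** The plan states no figure on this point, so there is none to reproduce. The check is a count of dose-timed recordings, followed by a test of whether the effect on the ECG means can be sized.

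**Count**

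| Recording | Visits | Timed to a dose? | Summary in 13.4? |
|---|---|---|---|
| Holter | 2 (first dose) | Yes | No |
| 12-lead ECG | 2 | Not stated to be pre-dose | Yes, by visit |
| 12-lead ECG | 3 to 14 | No | Yes, by visit |
| PK samples, 20 subjects | 7, 11, 14 | Yes | Yes (13.3.2), no ECG link |

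Visit 15 falls two to four weeks after the last dose and is off drug, so it is not counted.

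- Visits under repeated dosing: 3 to 14, which is 12 visits. With a dose-timed ECG: 0.
- If 60 subjects attend all of them: 60 × 12 = 720 tracings, none dose-timed by the plan.
- Subject-visits where the PK schedule already fixes time since dose: 20 × 3 = 60, or 60/720 = 8%.

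The source-data list in Section 11.2 asks for date and time of blood sampling but lists ECG without a time. No section asks for the time of the last home dose to be recorded with the ECG.

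**Can the dilution be sized?** The readable text gives no tmax, half-life or accumulation figure. The two calculations below are illustrations on assumptions.

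1. Suppose an untimed ECG falls uniformly within a 12-hour dosing interval. A peak window of w hours is then hit with probability w/12: 1/12 = 8% for one hour, 4/12 = 33% for four hours. The tracings that hit it could not be identified.

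2. Suppose the peak is at 1 h and the half-life is 1 to 4 h. The fraction of peak left at t hours is 2^(−(t−1)/half-life).

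| Time after dose | Half-life 1 h | Half-life 4 h |
|---|---|---|
| 2 h | 50% | 84% |
| 3 h | 25% | 71% |
| 6 h | 3% | 42% |
| 12 h | 0.05% | 15% |

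The answer runs from near-peak to almost nothing, depending on the clock time chosen, and the plan does not fix that time.

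**Does the first-dose Holter stand in for steady state?** On the same assumed kinetics, accumulation with 12-hourly dosing is 1/(1 − 2^(−12/half-life)).

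- Half-life 1 h: 1/(1 − 1/4096) = 1.0002.
- Half-life 4 h: 1/(1 − 1/8) = 1.14.

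The first-dose peak would be 87.5% to about 100% of the steady-state peak, and a window to at least 180 minutes would span a peak at 1 h. For a purely concentration-driven effect, the Holter could be a fair proxy. The documents neither confirm nor rule out these kinetics.

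**What timed ECGs could show.** With 20 subjects and an assumed SD of QTcF change of 10 to 20 ms, the two-sided 90% confidence interval has half-width 1.729 × SD/√20, which is 3.9 to 7.7 ms. That is enough to notice a large shift, not to exclude a small one.

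**The case against.** A reader might infer that the trial cannot show any cardiac effect of C21 under repeated dosing, or that such an effect would be understated by about 58% to nearly 100%. The documents support neither reading. The percentage range follows from choosing 6 h and 12 h after the dose and an assumed half-life; at 2 h or 3 h the same model retains far more of the peak. Those assumptions also imply little accumulation, so the first-dose Holter, which is not limited to the PK subset, would see most of the steady-state peak concentration. The text also does not say that visit-day doses are witnessed or that ECGs are taken on arrival.

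Other points on this side stand as well:

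- Untimed, centrally read ECGs at 12 visits can reveal gross or slowly developing changes, and some will fall near the peak by chance.
- Routine surveillance is in place: a cardiovascular examination at each of Visits 3 to 14 (8.2.4), rapid reporting of cardiac events (9.3) and an independent data monitoring committee (14).
- Section 3.5 cites exposure up to 200 mg twice daily for up to 8 days in healthy subjects, and Section 3.9 cites centrally read telemetry without clinically significant findings. Further cardiac rationale may lie in removed text.
- No objective or endpoint names QTc or a concentration-ECG relation, and Section 13 defers analysis detail to a separate SAP.

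These points lower the severity but do not remove the gap. Eight days in healthy subjects is not up to 36 weeks in IPF patients. Similar concentration at the first dose does not establish similar effect after weeks of exposure. A SAP can add a Holter summary but cannot recover dose times that were never collected.

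**Conclusion.** The point holds as a cheap improvement, not as a defect that undermines the primary safety objective. Three facts rest on the text alone: the Visit 2 Holter is the only dose-timed cardiac recording, Section 13.4 plans no summary of it, and none of the 12 repeated-dose visits has an ECG tied to a dose. It follows that a null by-visit mean on repeated dosing cannot be told apart from off-peak tracings. The plan provides no ECG that can be attributed to a known exposure after weeks of dosing in IPF patients.

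No size can be put on any dilution without a tmax and half-life. How well the first-dose Holter represents the steady-state peak is likewise open.

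**What to change.** - In Section 8.2.6 and Table 1, state that the Visit 2 12-lead ECG is taken before the first dose.
- For the PK-subset subjects at Visits 7, 11 and 14, take the already scheduled 12-lead ECG at one fixed post-dose PK sampling time: the one nearest the tmax known to the sponsor. A range of times would bring back part of the problem.
- At all other on-treatment visits, record the clock time of the ECG and of the last C21 dose.
- In Section 13.4.2 and the SAP, summarise the Visit 2 Holter. Separately from the pooled by-visit table, summarise change from the pre-dose Visit 2 ECG for the timed post-dose ECGs, alongside the matching plasma concentrations. Label this exploratory: at most 20 subjects, no control group and no control for time of day.

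The cost is schedule and eCRF wording, slight extra data entry and one added table or figure. It needs no added ECG, visit or central reading, and dosing is unchanged. The downside is that PK-subset ECGs at three visits follow a different timing from those of the other subjects, which the by-visit table should note. At this version's date (September 2021), enrolment was planned to Q1 2022 and the last visit to Q1 2023 (Section 6.4). A change made then would still reach later visits, though PK subjects already past Visit 7 or 11 would contribute fewer timed ECGs. The SAP can be settled up to database lock.
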